9. STUDY PATIENTS AND DEMOGRAPHICS

9.1 Disposition of Patients and Withdrawals

The numbers and percentage of patients screened, randomized, completing the study, and withdrawing from the study, along with reasons for withdrawal, will be tabulated overall and by treatment group. The number and percentage of patients in each analysis population will be reported. Additionally, the number and percentage of patients that have an investigator-directed dose reduction from two tablets per day to one tablet per day will be summarized. The disposition and withdrawal summaries will be based on all patients who have data entered into the database.

9.2 Protocol Violations and Deviations

Protocol deviations will be checked on complete data for all patients. Protocol deviations will be summarized by type, status as Important vs Non-important, and by treatment group for the Safety population.

Individual patients with protocol deviations or violations will be listed.

9.3 Demographics and Other Baseline Characteristics

Descriptive summaries of the demographic and other baseline characteristics will be completed for all enrolled patients in the study population by treatment groups, unless otherwise specified.

Descriptive summaries of demographic and other baseline conditions will include:

- Demographics (age, gender, race/ethnicity, height, weight, BMI, family status, education and employment status)
- Tobacco/nicotine, alcohol, and THC/cannabis use history

Medical History will be coded using version 23.0 of the Medical Dictionary for Regulatory Activities (MedDRA) and summarized by SOC and Preferred Term using frequency counts by treatment group. Physical examination data, as well as findings from dedicated oral cavity examinations, will be presented in listings.

Protocol: TNX-CY-F307 Page 26 of 45

Final v1.0

10. EFFICACY ANALYSES

10.1 Primary Efficacy Analysis

10.1.1 Estimand

The primary ITT analysis will provide an estimate of the following causal estimand: the difference in the weekly mean change from Baseline of the daily patient self-reported 24-hour recall average pain severity rating using an 11-point (0-10) NRS evaluated at the Week 14 endpoint in all randomized patients attributable to the initially randomized treatment assignment, under the assumption that those withdrawing due to AEs and lack of efficacy revert to the baseline pain levels (on average).

10.1.2 Primary Analysis

The mean change from baseline in the weekly average of daily pain scores from baseline to each week in the TNX-102 SL and placebo arms will be analyzed using a restricted maximum likelihood (REML) based repeated measures approach with data imputed using multiple imputation (see Section 8.1.4). Week 14 will serve as the primary time point of interest. Models will be run on each of the twenty imputation sets individually and will include the fixed, categorical effects of treatment, pooled site, study week, and treatment by study week interaction, as well as the fixed covariates of baseline value and baseline value score-by-study week interaction. An unstructured covariance structure will be used to model the within-patient errors. If this analysis fails to converge, the following structures will be tested in this order: first order ante dependence, heterogeneous first order autoregressive, heterogeneous compound symmetry and compound symmetry with the first to give convergence used. The Kenward-Roger approximation will be used to estimate the denominator degrees of freedom. LS means and differences across the twenty MI reps will be combined using SAS procedure MIANALYZE (Rubin, 1976). Significance testing will be based on least-squares means and two-sided 95% confidence intervals will be presented. The p-values will be compared against two-sided alpha of 0.05.

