8.1.1 Adjustments for Multiplicity

8.1.1.1 Multiplicity

To adjust for multiplicity and to control for overall type I error, a sequential test procedure will be applied to the primary and key secondary efficacy endpoints. If the primary analysis produces a result that is statistically significant at the two-sided 0.05 level, a significance level of 0.05 will be used for comparing the secondary endpoints in an ordered fashion. If the analysis for a secondary endpoint does not produce a statistically significant result (p-value < 0.05), then the remaining secondary endpoint analyses will automatically be considered non-significant regardless of the p-value produced.

The order of key secondary endpoints in which they are to be tested is as follows:

- Proportion of patients with a PGIC rating of "very much improved" or "much improved" at Week 14
- Change from baseline in the FIQR symptoms domain score at Week 14
- Change from baseline in the FIQR function domain score at Week 14

Protocol: TNX-CY-F307 Page 18 of 45

Final v1.0

- Change from baseline in the PROMIS score for sleep disturbance at Week 14
- Change from baseline in the PROMIS score for fatigue at Week 14
- Change from baseline to Week 14 in the weekly average of the daily diary assessment of sleep quality.

No other adjustments for multiplicity will be made and other p-values displayed in the output will be considered for descriptive summary purposes only and will not be used for formal inference. Additional details regarding statistical analysis for the listed endpoints can be found in Section 10.

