8.1.4 Imputation of Missing Data

For individual daily pain scores, since a mean is used in the calculation of the primary endpoint, it is not necessary to replace values missing on random intermittent days; weeks will have average values as long as a single value for that week is present.

Daily sleep diary data will be handled in an identical manner to the pain scores.

Continuous outcomes included in the list of key secondary outcomes that are collected in-clinic will be handled as above, minus the step of creating weekly averages of daily values and with steps being done by visit instead of week.

Patients with missing PGIC at a given visit will be considered non-responders at that visit for the purposes of treatment comparisons and efficacy claims; additional tabulations will summarize the number and percentage in each category out of non-missing values as well as a count of the missing values.

No missing safety data will be imputed.

Protocol: TNX-CY-F307 Page 20 of 45

Final v1.0

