10.2 Secondary Efficacy Analyses

Secondary efficacy analyses will be based on the ITT population only.

Continuous Endpoints

For the purposes of possible label claims and reported p-values entered into the multiplicity algorithm, an approach identical to the primary analysis will be used for all continuous outcomes. See Section 8.1.4 for the imputation algorithm and Section 10.1.2 for the analysis approach.

Outcomes using these analyses will include:

- Change from baseline in the FIQR symptoms domain score
- Change from baseline in the FIQR function domain score
- Change from baseline in the PROMIS score for sleep disturbance
- Change from baseline in the PROMIS score for fatigue
- Change from baseline in the weekly average of the daily diary assessment of sleep quality.

For each, all time points will be summarized, but the primary time point of interest is Week 14. Time points other than Week 14 are considered exploratory. The estimand for each is identical to the primary, substituting for the endpoint in question.

For the sleep quality assessment collected via a daily patient diary, the baseline score and the weekly scores for each patient will be calculated as the weekly average score based on the mean of the scores recorded for that study week (Section 8.2.2).

In addition to the above analyses using the primary imputation and model, analyses will be repeated on the outcomes above, but using observed data only without imputation.

Categorical Endpoints

A categorical analysis of PGIC will compare the treatment arms with a difference in proportions Z test (equivalent to a Pearson's Chi Squared). Patients with results of "very much improved" or "much improved" (defined as responders) will be compared to all other categories (defined as non-responders). Patients with missing data will be considered non-responders. The percentages of responders and the 95% CIs of the percentages as well as the difference in the percentages and its 95% CI will be reported. A summary of frequency counts for all PGIC responses for each time point will be presented; Week 14 is of primary interest and all other time points are considered exploratory.

Protocol: TNX-CY-F307 Page 28 of 45

Final v1.0

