15.4 Appendix D

The following list of numbers will be used for random seeds where required for MI processes:

These will generally be used in order for the primary analysis, then secondary endpoints and sensitivity analyses. For cases where identical code may be applied to more than one outcome or a sensitivity analysis that uses a minor variation on the primary code, the second to last digit will be incremented by 1 to produce new seeds for the subsequent outcome/analysis. If a single dataset requires more than the 10 seeds above, additional seeds will be generated by incrementing the last digit in the last by 1. All seeds used will be documented in the programming specifications and the programs themselves.

Protocol: TNX-CY-F307 Page 44 of 45

Final v1.0

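### Twenty imputations give a valid test, but leave verdicts near 0.05 on the primary and five continuous key secondaries partly dependent on an arbitrary seed list

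*SAP*

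**What the plan says.** SAP 10.1.2 analyses weekly pain by a repeated measures model on multiply imputed data: "Models will be run on each of the twenty imputation sets individually". The results are then pooled: "LS means and differences across the twenty MI reps will be combined using SAS procedure MIANALYZE". The decision rule follows: "The p-values will be compared against two-sided alpha of 0.05".

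SAP 10.2 states that "an approach identical to the primary analysis will be used for all continuous outcomes". These are the two FIQR domains, the two PROMIS scores and diary sleep quality, and their p-values enter the multiplicity algorithm. PGIC, the first key secondary, is handled differently in SAP 8.1.4: "Patients with missing PGIC at a given visit will be considered non-responders at that visit". It therefore carries no imputation randomness.

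Under SAP 8.1.1.1, once a key secondary fails at 0.05, the "remaining secondary endpoint analyses will automatically be considered non-significant regardless of the p-value produced". Appendix D pre-specifies the seeds: "The following list of numbers will be used for random seeds where required for MI processes". It gives later outcomes and analyses their own incremented seeds.

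The available text gives no reason for choosing twenty, no target for Monte Carlo error and no rule for raising the number. The seed values and what appears to be part of SAP 8.1.4 are not visible in the public text. Nothing is held against the plan on that account.

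**The concern.** Multiple imputation draws the missing values at random. Some of the variation comes from the rule in SAP 10.1.1 that the estimand is defined "under the assumption that those withdrawing due to AEs and lack of efficacy revert to the baseline pain levels", on average. A pooled estimate from a finite number of sets therefore has a Monte Carlo error that comes from the seeds, not from the patients. Fixed seeds make the run repeatable, but the result still depends on which list was written down.

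A hard threshold makes this matter. Of the seven tests in the sequence, six (the primary and five continuous key secondaries) are exposed. If the seeds decide one of them, they also decide whether every later test is open. The usual reassurance, a relative efficiency near 1, describes average precision. It does not say how far a single p-value moves between seed lists.

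**Working it through.** **Inputs from the documents.** Number of sets m = 20 and two-sided alpha 0.05 (SAP 10.1.2); 470 patients, 235 per arm (SAP 6); exposed tests 1 + 5 = 6 of 1 + 6 = 7 (SAP 8.1.1.1 and 10.2).

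**Assumptions.** FMI from 0.1 to 0.4 (0.05 also tried). Complete-data degrees of freedom 440. Power of 80% or 90%, because the available text gives no effect size, SD, power or dropout rate. There is no figure for Monte Carlo error in the plan to reproduce.

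**Step 1: Monte Carlo SD of the pooled estimate.** In units of its standard error this is about sqrt(FMI/m).

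- m = 20: sqrt(0.1/20) = 0.07; sqrt(0.2/20) = 0.10; sqrt(0.4/20) = 0.14.
- m = 200: sqrt(0.1/200) = 0.02; sqrt(0.2/200) = 0.03; sqrt(0.4/200) = 0.04.

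Relative efficiency, 1/(1 + FMI/m), at m = 20 is 1/1.005 = 0.995 for FMI 0.1 and 1/1.02 = 0.980 for FMI 0.4.

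**Step 2: validity.** Rubin's rules use the total variance U + (1 + 1/m)B, where U is the within-imputation and B the between-imputation variance. The 1/m term pays for the finite number of sets. Simulated type I error, with Barnard-Rubin degrees of freedom, is about 0.049 to 0.050 at both 20 and 200 sets.

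**Step 3: disagreement averaged over trials.** For each simulated trial the pooled test was run with two independent seed lists. The table shows the percentage of trials in which the two verdicts on a single test differ. Repeat runs vary by about 0.1 point.

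| FMI | 80% power, m = 20 | 80% power, m = 200 | 90% power, m = 20 | 90% power, m = 200 |
|---|---|---|---|---|
| 0.1 | 2.6 | 0.8 | 1.6 | 0.5 |
| 0.2 | 3.9 | 1.2 | 2.5 | 0.7 |
| 0.3 | 5.2 | 1.5 | 3.4 | 1.0 |
| 0.4 | 6.5 | 1.9 | 4.2 | 1.2 |

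**Step 4: direction.** At 80% power, compared with unlimited imputations, twenty sets lose significance in 1.0% of trials and gain it in 0.8% at FMI 0.1. At FMI 0.2 the figures are 1.7% and 1.1%. The net loss of power per test against 200 sets is 79.93 - 79.70 = 0.2 percentage points at FMI 0.1 and 79.61 - 78.20 = 1.4 points at FMI 0.4.

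**Step 5: conditional on the p-value that unlimited imputations would give.** The table shows the percentage chance that one run returns p >= 0.05.

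| Limiting p | FMI 0.1, m = 20 | FMI 0.2, m = 20 | FMI 0.1, m = 200 | FMI 0.2, m = 200 |
|---|---|---|---|---|
| 0.04 | 13 | 25 | about 0 | 0.7 |
| 0.03 | 0.5 | 5.4 | 0 | 0 |
| 0.02 | 0 | 0.3 | 0 | 0 |
| 0.01 | 0 | 0 | 0 | 0 |

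For a limiting p of 0.04, the shortcut Phi((1.96 - 2.05)/sqrt(FMI/m)) gives only 10% and 18% in the m = 20 columns. It leaves out the error in estimating B and the degrees of freedom, so the simulated values are used. At FMI 0.3 and a limiting p of 0.04, the simulated chance is 33% with 20 sets, 10% with 100 and 3% with 200.

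**The case against.** The strongest reply is that nothing here is an error. Twenty sets pooled by Rubin's rules give a test of the right size, and relative efficiency is 98% or better over the assumed range. The pre-specified seeds rule out choosing a list after seeing results. That all stands. A reader might infer that twenty sets inflate type I error or leave room for seed shopping. Step 2 and Appendix D show that neither inference is supported.

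A second reply is that the 13 to 25% figure assumes a limiting p of 0.04, next to the line. This also stands. That range is not the chance that this trial's verdict turns on the seeds; step 3 gives the relevant size. Nor does the noise only close gates: step 4 shows that it also opens them.

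Third, the SAP has analyses that would expose a fragile result. SAP 10.1.3 adds a tipping point analysis if the primary is significant, and SAP 10.2 repeats the continuous secondaries on observed data without imputation. These help interpretation but do not change the formal verdict. The tipping point search also ends, if it tips, at the 0.05 boundary, where Monte Carlo noise matters most.

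Fourth, no error target in the documents leads to 200 in particular. That is fair. The case for 200 is that it brings the noise to a low level at little cost. It is not a threshold for validity.

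**Conclusion.** The concern holds as a minor, cheap improvement. SAP 10.1.2 and 10.2 leave six of seven gated tests with avoidable random error. That error affects the stability of verdicts close to 0.05, not bias or test size. At FMI 0.1 to 0.4, moving from 20 to 200 sets cuts the chance that two seed lists disagree on one test by roughly a factor of three (for example 2.6/0.8 and 6.5/1.9 at 80% power). For a limiting p of 0.02 or less, the risk of losing significance is negligible at FMI up to 0.2.

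These sizes rest on the assumed FMI, power and degrees of freedom, none of which the documents give. If FMI is 0.05, the effect is smaller: for a limiting p of 0.04, 95% of runs with twenty sets give p between 0.031 and 0.051. The figures are per test and should not be multiplied by six, because the endpoints are correlated and later tests matter only if earlier ones succeed.

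**What to change.** Before unblinding, replace twenty in SAP 10.1.2, in both places and wherever else the number is repeated, with at least 200 imputations. Apply this to the primary analysis, the five continuous key secondaries and the imputation-based sensitivity analyses in SAP 10.1.3. Report the Monte Carlo error of each pooled estimate and p-value beside the result. Keep the pre-specified seeds. The timing matters because raising the number after seeing a p-value near 0.05 would look data-driven.

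The cost is a minor SAP revision and more computing, with 200/20 = 10 times as many model fits per endpoint. Each fit must be checked for convergence under the fallback order in SAP 10.1.2. The weekly pain model with unstructured covariance has 14 x 15/2 = 105 covariance parameters, so some added convergence checking should be expected. The estimand, model and patient procedures do not change.

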10.1.3 Sensitivity Analyses

Four sensitivity analyses will be performed:

For the first, pain scores will be censored on the day(s) on which an opioid is utilized. If the patient utilizes an opioid for any indication, then the pain score on each impacted day will be replaced by the score obtained on the day immediately prior to the first day of opioid use (and until the opioid is no longer used). This will be done prior to the weekly averaging, and all other calculations will be performed as described in the primary. This will investigate whether use of concomitant opioids influences the interpretation of study results.

For the second, patients that discontinue due to "withdrawal of consent" or "investigator decision" will be grouped with the LOE and AE dropouts when performing the multiple imputation procedure. This analysis will investigate whether the categorization of these reasons for dropout influences the interpretation of study results.

For the third, ALL patients that discontinue will be grouped with the LOE and AE dropouts when performing the multiple imputation procedure. This analysis will sample from the baseline

Protocol: TNX-CY-F307 Page 27 of 45

Final v1.0

distribution of all dropouts and will investigate whether treating dropouts as treatment failures (on average) influences the interpretation of study results.

Finally, a tipping point analysis will be performed on the values for the primary analysis. A shift parameter will be applied to the active treatment arm starting at .25 and increasing in increments of .25 through either 5 or when the outcome is no longer significant. This will only be performed if the primary analysis is significant. This will test the overall robustness of the primary analysis.

10.2 Secondary Efficacy Analyses

Secondary efficacy analyses will be based on the ITT population only.

Continuous Endpoints

For the purposes of possible label claims and reported p-values entered into the multiplicity algorithm, an approach identical to the primary analysis will be used for all continuous outcomes. See Section 8.1.4 for the imputation algorithm and Section 10.1.2 for the analysis approach.

Outcomes using these analyses will include:

- Change from baseline in the FIQR symptoms domain score
- Change from baseline in the FIQR function domain score
- Change from baseline in the PROMIS score for sleep disturbance
- Change from baseline in the PROMIS score for fatigue
- Change from baseline in the weekly average of the daily diary assessment of sleep quality.

For each, all time points will be summarized, but the primary time point of interest is Week 14. Time points other than Week 14 are considered exploratory. The estimand for each is identical to the primary, substituting for the endpoint in question.

For the sleep quality assessment collected via a daily patient diary, the baseline score and the weekly scores for each patient will be calculated as the weekly average score based on the mean of the scores recorded for that study week (Section 8.2.2).

In addition to the above analyses using the primary imputation and model, analyses will be repeated on the outcomes above, but using observed data only without imputation.

Categorical Endpoints

A categorical analysis of PGIC will compare the treatment arms with a difference in proportions Z test (equivalent to a Pearson's Chi Squared). Patients with results of "very much improved" or "much improved" (defined as responders) will be compared to all other categories (defined as non-responders). Patients with missing data will be considered non-responders. The percentages of responders and the 95% CIs of the percentages as well as the difference in the percentages and its 95% CI will be reported. A summary of frequency counts for all PGIC responses for each time point will be presented; Week 14 is of primary interest and all other time points are considered exploratory.

Protocol: TNX-CY-F307 Page 28 of 45

Final v1.0

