7.3. Number of Patients and Treatment Assignment

Approximately 470 patients will be randomized in a 1:1 ratio to treatment with TNX-102 SL 5.6 mg (2 x 2.8 mg tablets) or SL placebo tablets. Randomization will be stratified by center. Randomized patients who withdraw will not be replaced. Each patient will participate for 17-21 weeks in an outpatient clinic setting. This includes a variable 1 to 5-week screening and washout period, a 14-week treatment period, and a 2-week safety follow up period.

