13.4.4. Secondary Efficacy Analyses

Secondary efficacy analyses will be based on the ITT population only. For PGIC, patients with a "very much improved" or "much improved" response at the Week 14 endpoint will be considered responders. Patients with results in any other category or who discontinue early will be considered non-responders. A categorical analysis of PGIC responder status (yes/no) will compare the treatment arms with a difference in proportions Z test (equivalent to a Pearson's Chi Squared). The percentages of responders and the 95% CIs of the percentages as well as the difference in the percentages and its 95% CI will be reported.

Analysis of continuous secondary endpoints and adjustments for missing data will be described in detail in the SAP. Significance tests of treatment differences will be tested at the two-sided 0.05 level and corresponding 95% confidence intervals will be calculated.

To adjust for multiplicity and to control for overall type I error, a sequential test procedure will be applied to the efficacy endpoints. If the primary analysis produces a result that is statistically significant at the 0.05 level, a significance level of 0.05 will be used for comparing the secondary endpoints in an ordered fashion. If the analysis for a secondary endpoint does not produce a statistically significant result at the 0.05 level, then the remaining secondary endpoint analyses

will automatically be considered non-significant regardless of the p-value produced. The order in which the secondary endpoints are to be tested will be specified in the SAP.

No other adjustments for multiplicity will be made and other p-values displayed in the output will be considered for descriptive summary purposes only and will not be used for formal inference. Full details regarding the statistical analyses for the listed endpoints, including graphical presentations, can be found in the SAP.

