4.2 Method of Treatment Assignment and Randomization

The following randomization criteria must be satisfied at the Baseline visit (Visit 2) in order for the patient to continue in the study and be randomized:

- 1. The patient continues to meet all inclusion and exclusion criteria, including urine and blood test results and is successfully and consistently utilizing the diary system.
- 2. Patient's FM pain satisfies the following criteria, as assessed by diary pain scores (24 hour recall):
 - a. A mean pain intensity score ≥4 and ≤9 on the 11-point (0-10) NRS scale for the 7 days immediately preceding Visit 2, and
 - b. No more than 2 individual days with a score <4 on the 7 days immediately preceding Visit 2, and
 - c. No score of 10 on any of the 7 days immediately preceding Visit 2, and

Protocol: TNX-CY-F307 Page 15 of 45

Final v1.0

d. Pain scores must be recorded on at least 5 out of the 7 days immediately preceding Visit 2.

Before the start of the study, a computer-generated randomization schedule will be prepared. Based on the randomization schedule, eligible patients will be randomly assigned in a 1:1 ratio to receive TNX-102 SL tablets or placebo tablets for 14 weeks.

Treatment A: For Days 1-14, 1 tablet of TNX-102 SL 2.8 mg taken sublingually (under

the tongue) each day at bedtime. For Days 15-98, 2 tablets of TNX-102 SL 2.8 mg (5.6 mg) taken simultaneously and sublingually each day at bedtime.

Treatment B: For Days 1-14, 1 tablet of placebo taken sublingually (under the tongue)

each day at bedtime. For Days 15-98, 2 tablets of placebo taken

simultaneously and sublingually each day at bedtime.

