8.1.3 Site Covariate

For the purposes of modeling and imputation, all sites with less than 10 patients will be pooled into a single large site. In listings and analyses by site, patients will appear under their study site identifier (not the pooled site).

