10.3 Exploratory Analyses

All efficacy analyses at time points other than Week 14 are considered exploratory as described above.

Additional exploratory efficacy endpoints include:

- FIQR total score, overall impact domain score, and individual item scores at all post-randomization clinic visits
- Proportion of patients with a $\ge 30\%$ improvement from baseline to Weeks 1-14 in the daily self-reported pain severity score
- Proportion of patients with a ≥50% improvement from baseline to Weeks 1-14 in the daily self-reported average pain severity scores
- Proportion of patients with a PGIC rating of "minimally improved," "very much improved" or "much improved" at all post-randomization clinic visits
- PGIC as a continuous variable with 1-7 scoring
- CSFQ-14 at Week 14
- In-clinic assessment of pain (24-hour & weekly recall)

The PGIC, 30% and 50% improvement responder endpoints will be analyzed with a difference in proportions Z test (equivalent to a Pearson's Chi Squared). Patients with missing data will be considered non-responders. The percentages of responders and the 95% CIs of the percentages as well as the difference in the percentages and its 95% CI will be reported.

In addition to the responder analysis in the secondary outcomes, PGIC will be analyzed as a continuous variable scoring the responses 1-7. Results will be reported by treatment with summary statistics and an MMRM Model will be used to compare treatments. The model will include the fixed, categorical effects of treatment, pooled site, study week, and treatment by study week interaction. An unstructured covariance structure will be used to model the within-patient errors. If this analysis fails to converge, the following structures will be tested in this order: first order ante dependence, heterogeneous first order autoregressive, heterogeneous compound symmetry and compound symmetry with the first to give convergence used. The Kenward-Roger approximation will be used to estimate the denominator degrees of freedom. Significance testing will be based on least-squares means using a two-sided alpha=0.05 test and two-sided 95% confidence intervals will be presented.

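### The gatekeeping PGIC responder test ignores the center stratification used in randomization, so it is mildly conservative if response differs between sites

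*SAP*

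**What the plan says.** Protocol 7.3: "Randomization will be stratified by center". SAP 4.2 gives the 1:1 ratio without repeating the stratification, so that fact rests on the protocol; nothing in the SAP contradicts it.

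The primary model in SAP 10.1.2 contains "fixed, categorical effects of treatment, pooled site, study week, and treatment by study week interaction". SAP 10.2 carries the same approach over to the five continuous key secondaries. For modeling, SAP 8.1.3 states that "all sites with less than 10 patients will be pooled into a single large site".

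For PGIC response (the two best categories, missing counted as non-response), SAP 10.2 states: "A categorical analysis of PGIC will compare the treatment arms with a difference in proportions Z test". Protocol 13.4.4 has the same test: "A categorical analysis of PGIC responder status (yes/no) will compare the treatment arms with a difference in proportions Z test". Neither includes a site term. The exploratory analysis of PGIC as a 1-7 score does adjust for site (SAP 10.3): "The model will include the fixed, categorical effects of treatment, pooled site, study week, and treatment by study week interaction".

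PGIC response is the first key secondary in the fixed sequence. If a secondary test fails, the "remaining secondary endpoint analyses will automatically be considered non-significant regardless of the p-value produced" (SAP 8.1.1.1).

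**The concern.** Of the seven tests in the confirmatory sequence (the primary and six key secondaries), only PGIC response leaves out the factor that the randomization is stratified by. The same instrument is site-adjusted where it is exploratory and unadjusted where it supports a claim. The visible text gives no reason and shows no site-adjusted analysis of PGIC response. SAP 10.5 is blank in the public copy, so the absence can be asserted only for what is shown.

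Stratifying by center keeps the arms close to balanced within each site, so differences in response between sites largely cancel from the treatment comparison. An unstratified standard error still counts them. The confidence interval is then somewhat too wide and the test somewhat conservative. The stake is power at the step that opens the other five key secondaries. That gate exists under either test; the question is whether precision is given up there for no return.

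**Working it through.** **Inputs from the documents.** 470 patients, 235 per arm, 1:1 (Protocol 13.2, SAP 6); 30-40 sites (Protocol 7.1, SAP 4), so 470/40 = 11.8 to 470/30 = 15.7 patients per site; sites under 10 pooled (SAP 8.1.3); two-sided 0.05.

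**Assumed, because the visible text does not give them.** PGIC response rates, between-site spread, site sizes and block size. No stated PGIC power is available to reproduce; only 2 × 235 = 470 can be checked.

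**Step 1: direction.** The planned statistic is Z = (p1 − p0) / √[p(1 − p)(1/n1 + 1/n0)]. The term p(1 − p) is the total binary variance, within-site plus between-site. Let ρ be the between-site share. With arms balanced within sites, the null variance of Z is about 1 − ρ, so

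true size ≈ 2 × [1 − Φ(1.96 / √(1 − ρ))].

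At 25% response with normal site effects on the logit:

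| Site SD | ρ | Size |
|---|---|---|
| 0 | 0 | 5.0% |
| 0.3 | 0.0165 | 4.8% |
| 0.5 | 0.044 | 4.5% |
| 0.8 | 0.1023 | 3.9% |

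For SD 0.8: √0.8977 = 0.947; 1.96/0.947 = 2.069; two-sided tail 3.9%.

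**Step 2: anchor with no site differences, 25% vs 37%.** Pooled p = 0.31. Null SE = √(2 × 0.31 × 0.69/235) = 0.0427. Unpooled SE = √[(0.25 × 0.75 + 0.37 × 0.63)/235] = 0.0423. Power = Φ[(0.12 − 1.96 × 0.0427)/0.0423] ≈ Φ(0.86) ≈ 80.5%. CI width = 2 × 1.96 × 0.0423 = 16.6 points. The simulation below gives 80.6% and 16.6.

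**Step 3: simulation.** 20,000 trials per scenario: 33 sites of unequal size (gamma, shape 3; about 11 sites and 66 patients fall under the pooling limit) and permuted blocks of 4 within site. Marginal rates are held at 25% vs 37% (25% in both arms for type I error), so only the gap between tests varies. Pooled-variance Z is compared with CMH on pooled sites without continuity correction. CIs are unpooled Wald and Mantel-Haenszel (MH) with Sato variance.

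| Site SD (logit) | 0 | 0.3 | 0.5 | 0.8 |
|---|---|---|---|---|
| 95% range of site placebo response | 25% | 15-37% | 11-46% | 6-58% |
| Type I error, Z | 4.8% | 5.0% | 4.6% | 4.0% |
| Type I error, CMH | 4.9% | 5.0% | 5.0% | 4.8% |
| Power, Z | 80.6% | 80.5% | 81.0% | 82.3% |
| Power, CMH | 80.5% | 80.9% | 81.9% | 84.6% |
| Gain, points (from unrounded values) | 0.0 | 0.3 | 0.9 | 2.3 |
| CI width, Wald (points) | 16.6 | 16.5 | 16.5 | 16.5 |
| CI width, MH (points) | 16.6 | 16.4 | 16.2 | 15.8 |
| CI coverage, Wald | 94.8% | 94.8% | 95.2% | 95.8% |
| CI coverage, MH | 94.8% | 94.6% | 94.8% | 94.8% |
| Only CMH significant | 0.5% | 0.9% | 1.3% | 2.5% |
| Only Z significant | 0.6% | 0.5% | 0.4% | 0.2% |

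Monte Carlo SE: about 0.3 points for power, 0.15 for type I error, 0.07-0.11 for the gain.

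**Step 4: sensitivity to the assumptions.**

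- At 30% response, 35 sites and blocks of 2, 4 or 6, the size of Z is 4.9-5.1% at SD 0, 4.6-4.7% at 0.5, 3.7-4.1% at 0.8 and 3.4-3.5% at 1.0. Runs with 30 and 40 sites at SD 0.5 and 1.0 agree.
- With 27% placebo response and a fixed odds ratio of 1.75, power for Z vs CMH is 80.9 vs 80.8, 79.9 vs 80.1, 77.2 vs 78.4, 71.4 vs 74.4 and 67.3 vs 72.3% at SD 0, 0.3, 0.5, 0.8 and 1.0. Both levels fall because a fixed within-site odds ratio implies a smaller marginal difference as sites spread out; the gap is what matters.
- A separate run at 25% vs 37% with 35 sites gives gains of −0.1, 0.4, 1.0 and 2.1 points at SD 0, 0.3, 0.5 and 0.8.

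No scenario showed type I error inflation for the planned test.

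**The case against.** The planned test is valid, fully pre-specified and identical in both documents, and any error is on the conservative side. The plan is also consistent by endpoint type: binary endpoints, including the exploratory pain responders, get the Z test, and continuous ones get a model with site. The gain is under 1 point up to SD 0.5, rests wholly on assumed inputs, and reaches 2-3 points only at a spread that nothing in the documents suggests. Even with no site differences the tests disagree in 0.5 + 0.6 = 1.1% of trials, so raw disagreement overstates the relevance. The MH interval covers 94.6-94.8%, never quite 95%. The SAP is final and dated 17 October 2023, last patient completion was estimated for November 2023, and Protocol 15.1 requires ethics approval of protocol changes.

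Most of this stands as a limit on size. The net gain is the figure to use, and this is not an error of validity. It does not remove the point. Being binary is no reason to set the stratification factor aside, since a standard stratified test exists and the pooled sites are already defined. The coverage shortfall is within 0.4 points. The timing is a procedural cost: Protocol 13 leaves the full analysis description to a SAP finalized before database lock and unblinding.

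**Conclusion.** The concern holds as a matter of efficiency and consistency, not validity. The confirmatory PGIC test omits the randomization stratum that the other six tests in the sequence account for. If sites do not differ, nothing is lost. If they do, type I error falls below nominal (about 4.0% at SD 0.8) and power is lower than it need be, by less than 1 point up to SD 0.5 and by 2-3 points at 0.8. The choice of test changes the result at the gate in about 1-3 of 100 trials, with a net advantage of about 0-2 per 100 for the stratified test.

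These sizes depend on assumed response rates, site spread, site sizes and block size. The direction depends only on center-stratified randomization and some difference between sites. The change is worth making because it costs little and the test gates five endpoints; the trial's conclusions would not be unsound without it.

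**What to change.** In SAP 10.2, and in Protocol 13.4.4 to match, make the confirmatory Week 14 PGIC analysis a CMH test stratified by the pooled site of SAP 8.1.3. Report the Mantel-Haenszel risk difference with its 95% CI, keep missing as non-response, and retain the unstratified Z test as a sensitivity analysis. Applying the same method to the 30% and 50% pain responder endpoints is optional, for consistency only.

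The change must be fixed before unblinding and recorded in SAP 13 (Changes from Planned Analysis). It needs revised wording, a small programming change and, for the protocol text, the approval step in Protocol 15.1; no new data are needed. The statistical cost is that in 0.2-0.6% of simulated trials the Z test alone would have passed. With no site differences there is no gain and no measurable loss.
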